7.3 PLANNED ANALYSES

The statistical analysis will be based on the Treated Set (TS), which consists of patients who are randomised to a treatment group and receive at least one dose of randomised study medication.

Most analyses will be based on the treatment group (nintedanib only or nintedanib co-administered with sildenafil) as randomized. Safety parameters will be analyzed from an as treated perspective.

Although there is no per protocol set in the study, reasons for important protocol violations will be specified in the Trial Statistical Analysis Plan (TSAP). Patients with potential important protocol violations (those that relate to patient safety) will be identified at Blinded Review Planning Meetings and listed in the CTR and their impact will be evaluated.

7.3.1 Primary endpoint analyses

Change from baseline in SGRQ total score at week 12 will be analysed using REML based MMRM. The model will include fixed effect for treatment, visit and presence of any echocardiographic signs indicative of right heart dysfunction including right ventricular hypertrophy and right ventricular or atrial dilatation (as described in [section 6.2.1](#)), baseline SGRQ total score as a covariate and treatment-by-visit and baseline-by visit as interaction terms. Baseline SGRQ total score will be measured at visit 2. No imputation is planned if this assessment is not available for a patient. An unstructured (co)variance matrix will be used to model the within-patient measurements. In case there is a lack of convergence, a Compound Symmetry (co)variance matrix will be used. The Roger-Kenward approximation will be used to estimate denominator degrees of freedom. Data collected after visit 5 (planned 12 weeks after start of study treatment) will not be used for this analysis. Analyses will be implemented using SAS[®] Version 9.4 or higher. The primary treatment comparisons will be the contrast between treatments at 12 weeks.

Sensitivity analysis: The effect of missing data will also be investigated using tipping point sensitivity analyses. The technique will be detailed in the TSAP. The effect on the following subgroups will be explored:

- sex (female/male)
- age (<65, ≥65 years)
- race (White, Asian, Other)
- baseline FVC % predicted (<50%, ≥50%)
- baseline St. George's Respiratory Questionnaire (SGRQ) total score (≤40, >40)
- presence of any echocardiographic signs indicative of right heart dysfunction (yes/no)

Within subgroup analyses, subgroup (if not already included in the primary analysis model) and treatment subgroup interaction effect will be added to the primary analysis model. The treatment subgroup interaction effect will be of primary interest for subgroup analyses.

As needed, further details and/or further subgroups will be defined and described in the Trial Statistical Analysis Plan.

7.3.2 Secondary endpoint analyses

Change from baseline in UCSD SOBQ at week 12 will be analysed using the same method as the primary endpoint, but with baseline UCSD SOBQ instead of SGRQ total score as covariate. Data collected after visit 5 (planned 12 weeks after start of study treatment) will not be used for this analysis.

Both changes from baseline in SGRQ and UCSD SOBQ at week 24 will be analysed as in the respective week 12 analysis. For these analyses, data collected from the complete 24 weeks treatment period will be used.

Percentages of patients with on-treatment SAEs from baseline to week 24 will be compared using the Cochran-Mantel-Haenszel test adjusting for the categorical covariate presence of any echocardiographic signs indicative of right heart dysfunction (yes/no). Adjusted Mantel-Haenszel type risk ratios and risk differences with 95% confidence intervals will be used to quantify the treatment effect for the comparison between treatment groups.

7.3.4 Safety analyses

Analysis of key safety endpoints is described in [sections 7.3.2](#) and [7.3.3](#).

Adverse events will be coded using the Medical Dictionary for Regulatory Activities (MedDRA) coding dictionary. Standard BI summary tables and listings will be produced. All adverse events with an onset between start of treatment and end of the residual effect period (REP), a period of 28 days after the last dose of trial medication, will be assigned to the treatment period for evaluation.

All treated patients will be included in the safety analysis. In general, safety analyses will be descriptive in nature and will be based on BI standards. No hypothesis testing is planned.

Statistical analysis and reporting of adverse events will concentrate on treatment-emergent adverse events. To this end, all adverse events occurring between start of treatment and end of the residual effect period will be considered 'treatment-emergent'. The residual effect period is defined as 28 days. Adverse events that start before first drug intake and deteriorate under treatment will also be considered as 'treatment-emergent'.

Frequency, severity, and causal relationship of adverse events will be tabulated by system organ class and preferred term after coding according to the current version of the Medical Dictionary for Drug Regulatory Activities (MedDRA).

Laboratory data will be analysed both quantitatively as well as qualitatively. The latter will be done via comparison of laboratory data to their reference ranges. Values outside the reference range, as well as values defined as clinically relevant, will be highlighted in the listings. Treatment groups will be compared descriptively with regard to distribution parameters as well as with regard to frequency and percentage of patients with abnormal values or clinically relevant abnormal values.

Vital signs, physical examinations, or other safety-relevant data observed at screening, baseline, during the course of the trial and at the end-of-trial evaluation will be assessed with regard to possible changes compared to findings before start of treatment.

7.4 INTERIM ANALYSES

No interim analysis is planned but the conduct of the trial will be monitored by a DMC.

7.5 HANDLING OF MISSING DATA

In efficacy analyses of continuous endpoints missing data will not be imputed. In the analyses of the time-to-event endpoints, missing or incomplete data are managed by standard survival analysis techniques. These will be described in detail in the TSAP.

Missing or incomplete AE dates will be imputed according to BI standards. With respect to other safety evaluations, it is not planned to impute missing values.

In pharmacokinetic analyses, missing data will not be imputed. Descriptive statistics of concentrations at specific time points will be calculated only when at least 2/3 of the individuals have concentrations within the validated concentration range. The overall sample size to decide whether the “2/3 rule” is fulfilled will be based on the total number of samples intended to be drawn for that time point (i.e. BLQ, NOR, NOS, and NOA are included). Descriptive statistics of parameters are also calculated only when at least 2/3 of the individual parameter estimates of a certain parameter are available. If the actual sampling time is not recorded or is missing for a certain time point, the planned time will generally be used for this time point instead.

7.6 RANDOMISATION

Patients will be stratified by the presence of any echocardiographic signs indicative of right heart dysfunction including right ventricular hypertrophy and right ventricular or atrial dilatation (as described in [section 6.2.1](#)) and will be randomized in blocks to double-blind treatment. Approximately equal numbers of patients will be randomized to each treatment

group. BI will arrange for the randomization and the packaging and labelling of trial medication. The randomization lists will be generated using a validated system, which involves a pseudo-random number generator so that the resulting treatment will be both reproducible and non-predictable. The block size will be documented in the CTR. Access to the codes will be controlled and documented.

7.7 DETERMINATION OF SAMPLE SIZE

The hypothesis for expected difference in the change from baseline in SGRQ total score at week 12 is -4.5 units between nintedanib co-administered with sildenafil compared to treatment with nintedanib alone using a two group t-test with a 0.025 one-sided significance level.

The assumed difference is based on observations made in the INPULSIS[®] trials, where the observed mean change from baseline to week 12 in SGRQ total score when treated with nintedanib alone was 0.75/0.05 units with a standard deviation of 12.93/11.64 (INPULSIS[®]-1/INPULSIS[®]-2).

Based on the STEP-IPF trial [[R12-3686](#)], the mean change from baseline to week 12 in SGRQ total score when treated with sildenafil alone was -4.08 units with an estimated standard deviation of 11.02 units. It is assumed that the observed treatment effect remains stable when nintedanib is co-administered with sildenafil.

Therefore, power calculations are made based on the assumption of equal standard deviations among groups and an expected difference of -4.5 units.

Table 7.7: 1 presents the different scenarios for the sample size calculation.

Table 7.7: 1 Sample size calculations for difference in the change from baseline in SGRQ total score at week 12 assuming a group difference of -4.5 units for several standard deviations and a 1:1 randomisation ratio using a two group t-test with a 0.025 one-sided significance level.

	Standard deviation	N per group	Total sample size
80% power			
	11	95	190
	12	113	226
	13	132	264
90% power			
	11	127	254
	12	150	300
	13	177	354

So, a sample size of 125 patients in both groups will have about 90% power to detect a difference in means of -4.5 units in change from baseline in SQRG total score assuming that

the common standard deviation is 11 units using a two group t-test with a 0,025 one-sided significance level.

As we use a mixed model, including adjustment for several variable, this sample size based on t-test should provide at least 90% power.

Calculations were performed using nQuery Advisor[®] 6.1 statistical package by Statistical Solutions Ltd.

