1. INTRODUCTION

1.1 MEDICAL BACKGROUND

Idiopathic pulmonary fibrosis (IPF) is a rare disease of unknown aetiology that is characterized by progressive fibrosis of the interstitium of the lung, leading to decreasing lung volume and progressive pulmonary insufficiency [[P11-07084](#)].

The course of the disease in individual patients is variable: some patients progress rapidly, others have periods of relative stability punctuated by acute exacerbations and others progress relatively slowly. Acute exacerbations of IPF are events of respiratory deterioration of unidentified cause that occur in 5–10% of patients annually and are associated with a very poor outcome [[R12-2786](#)].

IPF is most prevalent in middle aged and elderly patients, and usually presents between the ages of 40 and 70 years. The median life expectancy in IPF patients after diagnosis is 2 to 3 years [[P11-07084](#)].

The latest update on clinical practice guideline for the treatment of IPF, jointly issued in 2015 by the American Thoracic Society (ATS), European Respiratory Society (ERS), Japanese Respiratory Society (JRS) and Latin American Thoracic Association (ALAT) has provided a conditional recommendation for treatment with nintedanib or pirfenidone for the majority of IPF patients, taking into account individual patient values and preferences [[P15-07362](#)]. Conventional IPF treatments such as n-acetylcysteine (NAC), corticosteroids, cyclophosphamide, cyclosporine and azathioprine are not approved treatments for IPF, and their efficacy is questionable or even harmful [[P15-07362](#); [P12-06085](#); [P14-07665](#)]. Non-pharmacological therapies such as pulmonary rehabilitation and long-term oxygen therapy are recommended for some patients, but their efficacy in patients with IPF has not been established. Lung transplant has been shown to positively impact survival in patients with IPF [[R11-5086](#); [R12-2785](#)]. Although the number of patients transplanted due to IPF has increased steadily over the last years, the scarce availability of donor organs, as well as the comorbidities and advanced age preclude many patients from referral to lung transplant [[R12-3676](#); [R12-3474](#)].

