6.2.3 Follow Up Period and Trial Completion

A follow-up (FUP) visit should be planned for 28 days after last trial drug administration. For detailed description of the trial procedures at the FUP visit, please refer to the flow chart.

Trial completion

The trial completion eCRF page has to be filled-in when the patient has terminated the trial. The end of the trial is:

- At the end of the follow-up visit for patients who have completed the trial on treatment as planned;
- After the early end of treatment (EOT) and follow-up visits, if a patient did not agree to come to the remaining planned study visits;
- At the end of visit 7 for patients who discontinued drug early but agreed to come to the remaining planned study visits.

Patients who prematurely discontinued trial medication

Patients who prematurely discontinue all study drugs (refer to [section 3.3.4](#)) before the planned end of treatment at visit 7, should come to the clinic as soon as possible after last drug intake for an early EOT visit. Reason for discontinuation must be documented in the eCRF. For detailed description of the trial procedures at this visit, please refer to the [flow chart](#).

In addition patients will be invited to attend all planned visits despite not being under treatment anymore and perform all study procedures except the laboratory tests (optional), biomarker sampling, pharmacokinetic sampling and the ECG. If patients don't accept to attend all remaining study visits, they will be contacted for vital status collection at week 24.

The need for coming to future visits in case of premature discontinuation of trial medication will be explained to patients prior to their participation in the trial.

Vital status information

In case of early discontinuation of all study drugs, if the patient does not agree to come to future visits as planned, every attempt will be made to get information on vital status at week 24 after his/her randomization.

Patients will be asked to agree to be contacted by the site personnel, which could be by telephone calls, to allow collection of this information.

If death occurs, the investigator will review the circumstances, including the relevant medical records to ascertain the most likely primary and secondary causes of death.

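### Does the protocol's claim of at least 90% power need changing because it states neither the covariate gain nor a missing-data rate?

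*Protocol*

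**What the plan says.** Protocol section 7.7 plans for a week-12 difference of 4.5 SGRQ units, a one-sided 0.025 t-test and 1:1 allocation. Its inputs come from earlier trials. For nintedanib alone, the two INPULSIS trials showed mean changes of "0.75/0.05 units with a standard deviation of 12.93/11.64". For sildenafil alone, STEP-IPF showed an improvement of "4.08 units with an estimated standard deviation of 11.02 units". The section concludes: "Therefore, power calculations are made based on the assumption of equal standard deviations among groups and an expected difference of -4.5 units". Table 7.7:1 lists the sample size for 80% and 90% power at SDs of 11, 12 and 13. The text then gives about 90% power for 125 per group at a common SD of 11, and closes with "As we use a mixed model, including adjustment for several variable, this sample size based on t-test should provide at least 90% power".

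The mixed model in section 7.3.1 contains the echocardiographic stratum, visit, and "baseline SGRQ total score as a covariate and treatment-by-visit and baseline-by visit as interaction terms". On missing data, section 7.5 says: "In efficacy analyses of continuous endpoints missing data will not be imputed". Section 6.2.3 limits the loss for patients who stop all study drugs: "In addition patients will be invited to attend all planned visits despite not being under treatment anymore". SAP section 7.4.1 uses these off-treatment observations in the primary analysis.

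**The concern.** The closing sentence turns an approximation into a floor. By t-test the plan falls just short of 90%, and the protocol's own table asks for 127 per group at SD 11 against the 125 planned. Reaching at least 90% therefore depends on the gain from covariate adjustment being larger than the loss from missing week-12 scores, and section 7.7 quantifies neither. Some loss is foreseeable. The patients have advanced disease, section 1.1 states "The median life expectancy in IPF patients after diagnosis is 2 to 3 years", and scores after death cannot be recovered. The nintedanib-alone SDs quoted in the same section are also above 11.

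The primary test opens the testing hierarchy in section 7.2. If power were well below what is stated, a true effect could be missed and the three SGRQ and dyspnea tests below it would become exploratory.

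**Working it through.** **Inputs from the protocol.** Difference 4.5, common SD 11, 125 per group, one-sided 0.025 (section 7.7); 5% two-sided in the analysis (section 7.2), which is equivalent here.

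**1. Reproduce the stated power.** Standard error = 11 × √(2/125) = 1.391. Noncentrality = 4.5/1.391 = 3.234, with 248 degrees of freedom and critical value 1.970. The noncentral t gives **89.6%**, which agrees with the stated figure of about 90%. The table also reproduces: 95, 113 and 132 per group for 80%; 127, 151 and 177 for 90%. The table has 150 in place of 151, which gives 89.9%.

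**2. Gain needed with complete data.** Adjustment multiplies the SD by √(1 − R²). Solving for 90% power at 125 per group gives R² = **0.012**, that is, an adjusted SD of 11 × √0.988 = 10.93.

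**3. Is 1.2% realistic?** Assume equal variances at baseline and week 12, with correlation r. Baseline then explains (1 − r)/2 of the variance of change. R² falls below 0.012 only if r exceeds 1 − 2 × 0.01225 = 0.975. The SD of change equals the baseline SD × √(2(1 − r)), so r = 0.975 with an SD of change of 11 requires a baseline SD of 11/√0.05 = 49 units. That is not credible for a score that section 7.3.1 splits into subgroups at 40. By the same formula, r = 0.8 implies a baseline SD of 17.4 and r = 0.9 implies 24.6.

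**4. Allow for missing scores (assumption).** The documents give no loss rate. If the 2-to-3-year median of section 1.1 is applied with a constant hazard, the proportion dead by day 84 is 1 − 0.5^((84/365.25)/m):

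- m = 2 years: 7.7%, leaving 115.4 per group;
- m = 3 years: 5.2%, leaving 118.5 per group.

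That median is for IPF in general and runs from diagnosis, so the true rate here could be higher or lower, and withdrawals would add to it.

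| Loss | No adjustment | r = 0.9 (R² 0.05) | r = 0.8 (R² 0.10) | R² needed for 90% |
|---|---|---|---|---|
| 0% | 89.6% | 91.1% | 92.4% | 1.2% |
| 5.2% | 88.0% | 89.6% | 91.1% | 6.4% |
| 7.7% | 87.2% | 88.8% | 90.4% | 8.9% |
| 10% | 86.3% | 88.0% | 89.6% | 11.2% |

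For losses of 5.2% to 7.7% and r of 0.8 to 0.9, the range is **88.8% to 91.1%**.

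**5. Direction of the approximation.** The table treats a patient without a week-12 score as contributing nothing. Under the same hazard only 1.8% to 2.6% die before day 28, so most of the others could supply a week-4 score to the mixed model. The SAP (Table 6.7: 2) accepts scores from day 58 as week 12, and by day 57 the assumed deaths are 3.5% to 5.3%. Both points move power upward.

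**6. Higher SDs.** Unadjusted, 125 per group gives 86.1% at a common SD of 11.64, 84.0% at 12, 78.3% at 12.93 and 77.8% at 13. These are correct but answer a different question, because the closing sentence follows directly from the one that fixes the SD at 11. Table 7.7:1 already brackets the position: at SD 12, 125 lies between 113 (80%) and 150 (90%); at SD 13 it is below the 132 needed for 80%.

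**The case for a change.** The best case for a change is that a general expectation of benefit from adjustment supports a direction, not a floor net of missing data. Whether the floor holds depends on figures the reader is not given. With r = 0.9 it survives only up to about 3.8% missing; with r = 0.8, up to about 8.8%. At 10% missing, 90% needs an R² of about 11%. Softening one word, or stating the two assumptions, would cost almost nothing.

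The factual part stands. Section 7.7 names no R², no correlation and no missing-data rate, and does not inflate the sample size. About 90% would have been the safer phrase. The case does not show that the trial is materially underpowered for its stated assumptions, and the sentence is itself hedged with the word *should*. A softer sentence that still says adjustment is expected to help would lack an R² just as much.

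The SDs of 11.64 and 12.93 carry more numerical weight, but section 7.7 claims no 90% at those values. Planning at 11 follows STEP-IPF (11.02), which section 1.2.2 describes as a trial in IPF with advanced lung function impairment. Section 3.2 says this trial's population is more impaired than that of INPULSIS, the source of the higher SDs. That is a defensible choice, and the table shows the reader what it costs if the SD is larger.

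**Conclusion.** No change follows. The t-test figure is right. At the planning SD of 11 with complete data, the stronger sentence holds under any plausible baseline correlation. With an assumed loss of 5.2% to 7.7% and an assumed correlation of 0.8 to 0.9, power is 88.8% to 91.1%, so the largest shortfall is about 1.2 points, and that is without credit for week-4 data. A larger loss would lower it further (88.0% at 10% missing with r = 0.9), but the documents give no basis for choosing a rate.

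What is missing is supporting detail for a planning statement. It does not enter the analysis: the sample size, the model, the alpha and the hierarchy are the same whether the sentence reads at least or about. A non-significant result would be judged mainly on the estimate and its confidence interval, not on this sentence. The conclusion assumes equal baseline and week-12 variances, an SD near 11, and that the quoted SDs are unadjusted, which the protocol does not say.

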8. INFORMED CONSENT, DATA PROTECTION, TRIAL RECORDS

The trial will be carried out in compliance with the protocol, the ethical principles laid down in the Declaration of Helsinki, in accordance with the ICH Harmonized Tripartite Guideline for Good Clinical Practice (GCP), relevant BI Standard Operating Procedures (SOPs), and relevant regulations and the Japanese GCP regulations (Ministry of Health and Welfare Ordinance No. 28, March 27, 1997) only for Japan.

Standard medical care (prophylactic, diagnostic and therapeutic procedures) remains in the responsibility of the treating physician of the patient.

The Investigator will inform the sponsor immediately of any urgent safety measures taken to protect the trial subjects against any immediate hazard, and also of any serious breaches of the protocol or of ICH GCP.

The rights of the Investigator and of the sponsor with regard to publication of the results of this trial are described in the Investigator contract. As a rule, no trial results should be published prior to finalization of the Clinical Trial Report.

For Japan only: The rights of the investigator / trial site and of the sponsor with regard to publication of the results of this trial are described in the investigator contract / trial site's contract. As a general rule, no trial results should be published prior to finalisation of the Clinical Trial Report.

The certificate of insurance cover is made available to the Investigator and the patients, and is stored in the ISF (Investigator Site File).

